8.2 Secondary endpoints

- Eight-week all-cause mortality (main secondary endpoint) among all participants enrolled. The numerator will be number of deaths during eight weeks after enrolment, the denominator is the number of participants enrolled. We will compare this indicator between both study arms. In addition, this endpoint will also be calculated considering right censored observation when a participant is lost to follow up during the observation period or a

This project is part of the EDCTP2 programme supported by the European Union

participant experiences a different event that makes further follow up impossible.

- Time to TB treatment initiation among microbiologically confirmed cases and among all TB cases since enrolment. We will estimate Kaplan Meier curves (event= TB treatment initiation among laboratory confirmed TB patients and among all TB cases) and hazard ratios at day 7, 14, 28 and 56. Additionally we will compare the time to related estimates (mean and standard deviation) of intervention and control group.
- Proportion of cases re-admitted to hospital. The numerator will be the number of admissions after initial discharge and within 8 weeks from enrolment. The denominator will be the number of participants enrolled.
- The proportion of participants who are diagnosed with TB (irrespective of bacteriological confirmation) and started TB treatment within 72 hours of enrolment. The numerator is the number of participants diagnosed with TB (with or without bacteriological confirmation) who started treatment within 72 hours of enrolment; the denominator is the number of participants enrolled.
- The proportion of participants who are diagnosed with microbiologically confirmed TB and are started on treatment at 7 days, 14 days, 4 weeks and 8 weeks of enrolment. In addition, this endpoint will also be calculated considering right censored observation when a participant is lost to follow up or dead during the observation period or a participant experiences a different event that makes further follow up impossible.
- Proportion of participants who are able to provide sputum, stool and urine samples for Ultra/AlereLAM testing within 24, 48 and 72 hours of enrolment (the numerator is the number of urine samples or (and) sputum samples provided within 72 hours of admission and the denominator is the number of patients enrolled).
- Time to laboratory confirmed TB diagnosis and any TB diagnosis since enrolment. We will estimate Kaplan Meier curves (events = laboratory confirmed diagnosis and any TB diagnosis) and hazard ratios at day 7, 14, 28 and 56. Additionally we will compare the time related estimates (mean and standard deviation) of intervention and control group.
- In-hospital and 4-week all-cause mortality as assessed by estimating a proportion (numerator: number of deaths occurring at the hospital over the number of enrolled participants and number of deaths by week 4 (irrespective of where it occurs) over the number of enrolled participants)
- Proportion of participants started on treatment without RIF resistance information (only AlereLAM positive)

The study has been powered to detect a statistically significant difference in the primary endpoint. Nonetheless, given that some patients might not present typical TB symptoms and TB misdiagnosis

This project is part of the EDCTP2 programme supported by the European Union

is frequent among admitted HIV-positive patients, we believe the intervention could be associated with a higher proportion of patients diagnosed with TB (irrespective of bacteriological confirmation) and thus, overall survival. In consequence, several secondary endpoints are related to survival at different time points.

8.3 Exploratory endpoints

- Diagnostic performance of a molecular TB diagnostic assay (Xpert Ultra and/or LumiraDx) on tongue swabs, and FujiLAM on urine against a microbiological reference standard (as defined in intervention arm) or against a composite reference standard that includes bacteriologically confirmation or/and clinical evidence resulting in therapy initiation. This endpoint will only be studied in participants of the intervention arm
- Diagnostic accuracy of CRP in blood in order to evaluate compared to TB symptom's screening in those with microbiologically confirmed TB.
- Comparison of primary and secondary endpoints of the intervention arm with the local standard of care at the sites before the study initiation (a retrospective data collection from consecutive HIV-positive patients admitted at participating hospitals).

This project is part of the EDCTP2 programme supported by the European Union

9. Trial Design and study arms

This is a multicentre, parallel, individually randomized controlled diagnostic trial in consecutively enrolled HIV positive adults to evaluate the impact of the extended use of Xpert Ultra (3 specimens) for TB diagnosis, using sputum, stool and urine, AlereLAM among consecutive PLHIV admitted to hospitals in 4 sites of 2 high burden African countries (Tanzania and Mozambique). Thus, the **intervention arm** for this trial will include TB testing performed irrespective of the presence of TB symptoms. Testing will be done on expectorated sputum, stool and urine with Ultra and urine with AlereLAM.

To fulfil exploratory objectives, we will also collect 2x tongue swabs for molecular TB diagnostic assay (Xpert Ultra and/or LumiraDx) testing, blood for CRP, and urine samples which will be stored for retrospective FujiLAM testing and analysis.

The **control arm** for this trial consist of patients managed according current WHO testing recommendations (as of Q1 2020) for HIV-positive inpatients. TB testing will be done as follows:

- a) ***Sputum Ultra*** whenever the patient has cough, fever, weight loss or night sweats and/or Ultra performed on any tissue (including lymph nodes) in patients with clinical suspicion of extrapulmonary TB.
and/or
- b) ***Urine Alere TB-LAM***, if patients have signs and symptoms of TB (pulmonary and/or extrapulmonary), or with advanced HIV disease or who are seriously ill or else irrespective of signs and symptoms of TB and with a CD4 cell count of less than 200 cells/mm³.

As part of a secondary objective, we will retrospectively collect data of a cohort of consecutively hospitalized HIV-positive patients that were admitted prior to the trial initiation (**third arm**), that will be used to compare the difference between the intervention arm or control arm with the real standard of care practiced at the sites.

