- Time to TB treatment initiation among microbiologically confirmed cases and among all TB cases since enrolment. We will estimate Kaplan Meier curves and hazard ratios at day 7, 14, 28 and 56. Additionally we will compare the time to related estimates (mean and standard deviation) of intervention and control group.
- Proportion of cases re-admitted to hospital. The numerator will be the number of admissions after initial discharge and within 8 weeks from enrolment. The denominator will be the number of participants enrolled.
- Proportion of participants who are diagnosed with TB (irrespective of bacteriological confirmation) and are started on TB treatment within 72 hours of enrolment.
- Proportion of participants who are diagnosed with microbiologically confirmed TB and are started on treatment at 7 days, 14 days, 4 and 8 weeks of enrolment.
- Proportion of study participants who are able to provide the different specimens (sputum, stool and urine samples) within 24, 48 and 72 hours of enrolment.
- Time to laboratory confirmed TB diagnosis and any TB diagnosis since enrolment. We will estimate Kaplan Meier curves and hazard ratios at days 7, 14, 28 and 56. Additionally we will compare the time related estimates (mean and standard deviation) of intervention and control group.
- In-hospital and 4-week all-cause mortality among all participants enrolled (assessed as the eight-week all-cause mortality).
- Proportion of participants started on treatment without Rif resistance information (only AlereLAM or FujiLAM positive)

Exploratory endpoints

- Diagnostic performance of a molecular TB diagnostic assay (Xpert Ultra and/or LumiraDx) on tongue swabs and FujiLAM on urine stool against a microbiological reference standard (defined as any test positive in the

This project is part of the EDCTP2 programme supported by the European Union

| | | | | | | | | | | | | | | | | | | | | | |
|---|---|---------------------------------------|------------|--------------------------------|----------------|-----------------------------|------------|---|-----------|--|-----------|---|-----------|--|------------|--|-------------|--|------------|--------------------------|-----------|

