| | 
intervention arm) or against a composite reference standard that includes bacteriologically confirmation or/and clinical evidence resulting in therapy initiation.
 
 Diagnostic accuracy of CRP in blood compared to TB symptom's screening in those with microbiologically confirmed TB. 
Comparison of primary and secondary endpoints of the intervention arm with the local standard of care at the sites before the study initiation (a retrospective data collection from consecutive PLHIV admitted at participating hospitals).
 
Sub-analysis
 
 Primary endpoint will be calculated at different intermediate timepoints (48 hours, 7 days and 14 days from enrolment). Primary and selected secondary endpoints will be calculated for participants' subgroups including CD4 cells/mm³ ≥200, <200 and <100, among participants with any TB symptoms, severely ill participants or with AHD, and among participants providing at least one sputum and (or) one urine sample for testing. | | | | | | | | | | | | | | | | | | | | |
| Study Timeline | 
  
 Estimated period for ethics clearance	May / 2022	
 
 Import permits and importation	Jan-May / 2022	
 
 Kick off / training meeting	Nov / 2021	
 
 Estimated date of first participant enrolled:	Sep/ 2022	
 
 Estimated date of last participant enrolled:	Jan/ 2024	
 
 Estimated date of last participant completed:	Mar/ 2024	
 
 Estimated date for end of data cleaning:	May / 2024	
 
 Estimated date for end of data analysis:	July / 2024	
 
 Estimated date for first manuscript draft:	Sep / 2024	
 
 Total duration of study:	47 months	
  
 | Estimated period for ethics clearance | May / 2022 | Import permits and importation | Jan-May / 2022 | Kick off / training meeting | Nov / 2021 | Estimated date of first participant enrolled: | Sep/ 2022 | Estimated date of last participant enrolled: | Jan/ 2024 | Estimated date of last participant completed: | Mar/ 2024 | Estimated date for end of data cleaning: | May / 2024 | Estimated date for end of data analysis: | July / 2024 | Estimated date for first manuscript draft: | Sep / 2024 | Total duration of study: | 47 months |

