Options that have been recommended by WHO to ensure earlier diagnosis and reduce mortality include strategic placement of rapid molecular TB diagnostics such as Xpert²¹ or Ultra²² within HIV care settings (which could enable availability of results within 24 hours), and uptake of the lateral flow urine lipoarabinomannan assay (LF-LAM)²³ strip-test – the Alere Determine™ TB LAM Ag (AlereLAM) for seriously ill PLHIV. However, despite AlereLAM being a cheap and fast test, only 9 of the 30 high TB and HIV burden countries have a national policy and algorithm indicating the routine use of urine LF-LAM (with various levels of implementation).² A recent study showed that urine-based TB screening of PLHIV admitted to hospital might reduce 56-day mortality in those with low CD4 counts, severe anaemia or clinically suspected tuberculosis.²⁴ A recently published meta-analysis showed that, as a screening test among PLHIV, AlereLAM has limited sensitivity of 45% (95% CI: 29-63) and specificity of 92% (80-97) against a composite microbiological reference standard.²⁵ However, screening with AlereLAM improves the likelihood of being diagnosed with TB during admission. The WHO recently expanded the recommendations for the use of AlereLAM to include adults, adolescents and children living with HIV with signs and symptoms of TB (inpatient and outpatient setting) or irrespective of signs and symptoms of TB with CD4 cell count under 200 cells/mm³ in inpatient settings irrespective of the CD4 cell count in outpatient settings.²⁶ The unavailability of CD4 counts upon admission or the assessment of the criteria for severely-ill or advanced HIV disease might delay quick testing of PLHIV in whom AlereLAM is recommended. In addition, LAM tests do not provide any information on potential resistance to anti TB drugs, which might hinder its implementation in high TB drug resistance settings.

The limitations of existing sputum-based tests for *M. tuberculosis* (*Mtb*) diagnosis create imperatives to explore the usefulness of easy to collect, non-respiratory specimens which could improve performance of all tests, while supporting treatment guidance and monitoring. In fact, the WHO has specified the need for rapid non-sputum based TB diagnostics among their high priority target product profiles for new TB diagnostics.²⁷

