5.3 Other promising tests and specimens

The Fujifilm SILVAMP TB LAM (FujiLAM)

A urine-based test which also detects LAM in urine, has shown promising results in frozen samples and is currently undergoing prospective evaluations in several settings. Recently published results using biobanked samples from studies conducted in South Africa showed higher sensitivity of FujiLAM compared to AlereLAM (70.4% vs 42.3%, using a microbiological reference standard), while maintaining high specificity.³¹ FujiLAM performance includes a 5-step procedure according to manufacturer's instructions and takes around 50-60 minutes from sample collection to results availability. Thus, it is also considered a true point of care test, since results could easily be handed out the same day the patient provides the sample.

This project is part of the EDCTP2 programme supported by the European Union

Given the substantially improved sensitivity of FujiLAM compared to AlereLAM, it could easily be the best test for immunosuppressed HIV positive patients, and has the potential for being an important tool for TB diagnosis in this population subgroup. In addition, it might have a potential to impact on mortality. A recent study in South Africa showed that FujiLAM conducted retrospectively predicted TB mortality among hospitalized patients.³⁷ However further studies in different populations and settings, with endpoints including patient important outcomes are needed to further assess its impact where it is most needed. The FujiLAM assay is undergoing a version change for large scale manufacturing. The new version will not be available until the end of the planned trial, so analysis for FujiLAM will be done retrospectively on banked urine samples collected as part of this study.

Oral swabs

As sputum can be difficult to collect in some patient groups, alternative specimens for TB diagnosis have been evaluated in recent years. In 2015, a study conducted in South Africa³⁸ demonstrated the presence of *M.tb* in oral swabs. The diagnostic performance of this sample collected in tongue dorsum that two samples per subject showed a combined sensitivity of 92.8% and specificity of 91.5%.³⁹ A recent study⁴⁰ showed lower sensitivity and specificity when collecting tongue swabs on different days (88%-94.4% and 79.2%, compared to sputum Xpert). However, despite these promising results, further validation studies are needed to assess the potential utility of these innovative specimens.

CRP

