8.1 Primary Endpoint(s)

The primary endpoint is:

- The proportion of participants diagnosed with microbiologically confirmed TB and started on TB treatment within 72 hours of enrolment, separately for intervention and control arm. The numerator is the number of participants per study arm who are diagnosed with microbiologically confirmed TB and start on treatment within 72 hours of enrolment. The denominator is the number of participants enrolled per study arm. We will compare this indicator between both study arms. Patients are defined to have microbiologically confirmed TB if at least one confirmatory TB test (Ultra, AlereLAM) gives a positive result.

Hospitalized PLHIV experience high mortality and TB underdiagnosis and misdiagnoses are frequent. TB diagnosis is important when you can quickly start appropriate therapy. This endpoint will capture both diagnostic dimensions of the intervention (higher rates of *Mtb* laboratory confirmation) as well as the relevant patient outcome (TB treatment initiated).

Diagnostic procedures and treatment initiation (if appropriate) should be completed within 72 hours of enrolment given the intervention is aimed at rapid collection of samples for all patients upon admission and that Ultra testing can provide results within a few hours from specimen collection at all participating sites.

The numerator of the primary endpoint also includes patients whose bacteriological confirmation might arrive after 72 hours of enrolment. There might be cases where liquid or solid culture might be requested and results arrive after 72 hours. If the patient had been put on treatment empirically (before a positive culture results has arrived), that case will contribute to the numerator, given that treatment would have been started in a "true" TB case.

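### The reference standard for FujiLAM accuracy includes AlereLAM, which has the same urinary target, and the wording does not keep tongue-swab Ultra out of its own reference

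*Protocol*

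**What the plan says.** Protocol section 8.3 assesses tongue-swab assays and "FujiLAM on urine against a microbiological reference standard (as defined in intervention arm", in the intervention arm only. That arm is tested with Ultra on sputum, stool and urine and with AlereLAM on urine (sections 9 and 10.9.1). Section 8.1 gives the confirmation rule: "Patients are defined to have microbiologically confirmed TB if at least one confirmatory TB test (Ultra, AlereLAM) gives a positive result".

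The synopsis words the same endpoint more broadly, "against a microbiological reference standard (defined as any test positive in the" and, continuing, "intervention arm) or against a composite reference standard that includes bacteriologically confirmation". The composite adds "clinical evidence resulting in therapy initiation".

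Section 5.3 describes FujiLAM as "A urine-based test which also detects LAM in urine". For AlereLAM, section 5.1 cites sensitivity of 45% and "specificity of 92% (80-97) against a composite microbiological reference standard". Protocol section 13.2.3 and SAP section 3.2 leave the exploratory analyses to separate SAPs, which are not among the documents.

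**The concern.** A reference standard should not share its errors with the test being assessed. Here a false AlereLAM line makes a participant reference-positive. If FujiLAM reacts to the same material, its error is recorded as a correct result. The two tests share a target and may share a specimen: section 12.1.3 takes the AlereLAM volume and the urine for storage from one collection, and FujiLAM is later run on banked urine (section 12.2.2).

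The composite is no way out. It includes bacteriological confirmation, so AlereLAM stays in. AlereLAM results also go to the clinicians who decide on treatment (sections 10.6 and 10.7), so AlereLAM enters a second time through treatment starts. No LAM-free reference appears anywhere. The two references are joined by an unranked alternative, so the choice between them could be made after results are seen.

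For tongue swabs the issue is different. The synopsis wording and the unrestricted Ultra in section 8.1 do not say that Ultra on a tongue swab is left out of the reference used to judge it. At stake is whether the FujiLAM and swab figures can be read as accuracy rather than partly as agreement with a related test.

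**Working it through.** **Plan's own figure.** The documents give no sample size or precision for these endpoints. The 586 per arm is used only as a denominator. It reproduces: 19% vs 26%, two-sided 5%, 80% power gives 558 per arm, and 558 × 1.05 = 585.9.

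**Illustration 1: how far sensitivity can move.** From the documents: N = 586, FujiLAM sensitivity 70.4% (section 5.3), AlereLAM specificity c = 92%, interval 80 to 97% (section 5.1). Assumed: true TB 20%, the reference captures every true case, and c is specificity against true TB.

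- True TB: T = 0.20 × 586 = 117.2. Without TB: 468.8.
- AlereLAM false positives entering the reference: F = (1 − c) × 468.8.
- FujiLAM positives among true TB: 0.704 × 117.2 = 82.51.
- Lowest apparent sensitivity (FujiLAM negative in all of F): 82.51/(T + F).
- Highest (FujiLAM positive in all of F): (82.51 + F)/(T + F).

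| c | F | T + F | Lowest | Highest | Reference-positive share |
|---|---|---|---|---|---|
| 97% | 14.06 | 131.26 | 62.9% | 73.6% | 22.4% |
| 92% | 37.50 | 154.70 | 53.3% | 77.6% | 26.4% |
| 80% | 93.76 | 210.96 | 39.1% | 83.6% | 36.0% |

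The 92% row gives a reference-positive share close to the planned 26%. The 80% row does not, and I would not rely on it.

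**Illustration 2: what an Ultra-only reference does.** AlereLAM 45%/92% and FujiLAM sensitivity 70.4% are from the documents. Assumed: true TB 26%, three-specimen Ultra sensitivity 75% and specificity 100%, FujiLAM true specificity 95% or 90%, and AlereLAM–FujiLAM dependence from none to maximal.

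- True TB 152.36; without TB 433.64; Ultra-positive 0.75 × 152.36 = 114.27; TB missed by Ultra 38.09.
- AlereLAM adds 0.45 × 38.09 = 17.14 true and 0.08 × 433.64 = 34.69 false positives, so the inclusive reference has 166.10 positives and 419.90 negatives.
- FujiLAM false positives at 95% specificity: 0.05 × 433.64 = 21.68.
- Ultra-only specificity: 1 − (0.704 × 38.09 + 21.68)/471.73 = 89.7%.
- Inclusive, no dependence: sensitivity (0.704 × 131.41 + 0.05 × 34.69)/166.10 = 56.7%; specificity 1 − (14.75 + 19.95)/419.90 = 91.7%.
- Inclusive, maximal dependence: sensitivity (80.44 + 17.14 + 21.68)/166.10 = 71.8%; specificity 1 − 9.67/419.90 = 97.7%.

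| FujiLAM true specificity | Reference | Apparent sensitivity | Apparent specificity |
|---|---|---|---|
| 95% | Ultra only | 70.4% | 89.7% |
| 95% | Ultra or AlereLAM | 56.7–71.8% | 91.7–97.7% |
| 90% | Ultra only | 70.4% | 85.1% |
| 90% | Ultra or AlereLAM | 57.8–79.6% | 87.0–95.6% |

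With AlereLAM in the reference, apparent specificity is above the Ultra-only value throughout, and it rises past the truth as dependence grows. The Ultra-only value is about 5 points too low, because TB that Ultra misses and FujiLAM finds is counted as false positive.

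**Wording side by side.** Sections 8.1 and 8.3 together give Ultra or AlereLAM, which leaves out FujiLAM and LumiraDx. They put no specimen limit on Ultra. The synopsis refers to any positive test in the arm, and swabs and FujiLAM urine are collected in that arm (section 11, table 2).

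**The case against.** The strongest reply has five parts.

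- **The analysis is deferred.** Separate exploratory SAPs may settle the reference. That stands, but the definition they would inherit is the one in the protocol.
- **The 92% was measured against an imperfect reference.** Some AlereLAM false positives may be real TB, and the 70.4% is likewise relative to a microbiological reference. This stands, and it is why the figures are illustrations only. The upper bound at 92% also needs FujiLAM to be positive in 8% of people without TB, whereas section 5.3 reports high specificity.
- **Reading controls exist.** Section 12.2.1 specifies a grade cut-off, two independent readers and a tie-breaker. These limit reading errors but not reactive material in the urine.
- **Ultra-only is not clearly better.** Illustration 2 supports this. Each reference errs in its own way, so neither should stand alone.
- **The stakes are low.** The endpoint is exploratory, and FujiLAM, run retrospectively, cannot influence treatment.

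Three stronger readings are tempting but not supported. First, a reader might infer from the synopsis that every index test sits in its own reference, making specificity 100% by construction. Sections 8.1 and 8.3 narrow the reference to Ultra and AlereLAM, so only tongue-swab Ultra is left unexcluded, and the arm's own testing is listed separately from the exploratory samples. Second, a reader might infer that added yield (section 7) cannot be answered. It can: FujiLAM positives among participants negative on Ultra and AlereLAM can be counted whichever reference is used. Third, the shared-LAM argument does not carry over to tongue swabs.

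**Conclusion.** The concern holds for FujiLAM. As written, AlereLAM-only positives count as TB in both references, no LAM-free reference is planned, and errors shared by the two LAM tests would be credited to FujiLAM. Apparent specificity is pushed up relative to a LAM-free reference; the direction for sensitivity depends on the dependence, which the documents do not give. At 92% AlereLAM specificity and the assumptions of illustration 1, apparent sensitivity ranges from 53% to 78% against 70.4%; at 97%, from 63% to 74%. The 39% to 84% range at 80% specificity should not be used, since it implies 36% reference positivity against the planned 26%.

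For tongue swabs the finding is one of wording: tongue-swab Ultra is not explicitly excluded from its own reference. That does not show an intention to include it. The primary comparison, mortality and the sample size are untouched.

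**What to change.** In the synopsis, section 8.3 and the exploratory SAP:

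1. Name the reference tests: Ultra on sputum, stool, urine or other clinical specimen, and AlereLAM. Use the same list in each place.
2. State that the index tests (FujiLAM, tongue-swab Ultra and LumiraDx) are excluded from the reference.
3. Pre-specify FujiLAM accuracy against an Ultra-only reference, reported side by side with the AlereLAM-inclusive and composite references.
4. Add a FujiLAM by AlereLAM cross-tabulation.

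Settle this before any FujiLAM or swab result is seen. The cost is wording; no test beyond those planned is needed, although stored urine may be incomplete because section 12.5 makes storage optional. The Ultra-only reference has fewer positives and wider intervals, and it understates FujiLAM specificity because TB found only by LAM counts as false positive. The report should say so beside the estimates.
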